5.2 Visit procedures

Below is a detailed description of each visit planned for the study. The Principal Investigator and/or his delegates will record each information first in the patient's medical record (or appropriate source document) and then in the eCRF.

Visit 1 (Screening): Day -90 to -1

- Informed Consent procedure completion, which has to be implemented before any trial procedures is performed
- Inclusion and exclusion criteria verification and confirmation
- Complete medical history, vital signs (BP, HR) collection and physical examination
- Pregnancy test (by serum or urine determination, according to Principal Investigator or hisdelegates decision) for women of childbearing potential or with amenorrhea ≤ 2 years
- Hematology examinations, which include: glucose, urea nitrogen, , creatinine, sodium, potassium, calcium, total
 cholesterol, HDL and LDL, triglyceride, , alkaline phosphatase, LDH, complete blood cell counts with differential and
 platelet counts, APTT, PT, INR, fibrinogen, VES, PCR
- ECG
- Pulmonary slab. In case the patient has performed a CT scan or RMN (because of the routinary assessment of the progression of the underlying disease) within at least 2 months from the ICF signature, the pulmonary slab will not be performed Liver function test includes: ALT, AST, ALP, bilirubin and total protein, Gamma-GT
- The determination of viral titres include: hepatitis B and C,. Tests to be performed only if not yet available within the medical history of the patient or if the relevant results need to be confirmed. HIV test is performed according to Principal Investigator or his delegates decision
- Concomitant medications recordings
- · Adverse event assessment and recording

Visit 2 (Baseline):- Day 0

- Laboratory test results evaluation
- Check and confirmation of the inclusion and exclusion criteria vs. the laboratory test results
- Randomization of the patient, according to the specific procedure implemented for the study
- Concomitant medications recordings
- · Adverse event assessment and recording

Visit 3 (Surgery):Day 1

- Evaluation of the appropriate target bleeding site in the hepatic parenchyma ("oozing" or "moderate")
- Recording of bleeding site characteristics (source of bleeding, bleeding severity using "oozing" or "moderate", approximate area of bleeding site)
- Recording of intraoperative details (hepatic parenchyma characteristics, intraoperative measurement of total
 volume of transfused blood products, duration of the surgery, type of hepatic resection, the estimated
 intraoperative blood loss and the use of Pringle's maneuver) Concomitant medications recordings
- Adverse event (intraoperative and not-intraoperative) assessment and recording

The patients randomized to Common Surgical Techniques (CST) will be treated conventionally while the patients randomized to experimental technique (CST + Hemopatch) will be treated conventionally with the adjunct of Hemopatch.

For patients included in ARM B Hemopatch is applied upon the verification made by the surgeon of the presence of an appropriate target bleeding (oozing or moderate) site in the hepatic parenchyma. At the time point of application a stopwatch starts simultaneously (time zero). Time to hemostasis is defined as the time required to obtain successful haemostasis in a single bleeding site. This time will be recorded by the operator delegated by the Principal Investigator and according to the surgeon's observation. At 3 minutes the inspection will be made and, if haemostasis is not

achieved, the treatment is considered failed and the Principal Investigator and/or his delegates is allowed to use additional haemostatic measures (including other topical haemostatic agents).

The time to haemostasis will be recorded before in the patient's medical record and then in the eCRF. The bleeding site will be observed for 1 additional minute (after the first 3 minutes) at the end of the haemostatic procedure and at the end of the surgery, in order to confirm the achievement of haemostasis. At the end of surgery at least one perihepatic Jackson-Pratt drain will be left near the site of resection.

Patients allocated to ARM A, will undergo the conventional hemostatic procedures and therefore also these patients will end up with a perihepatic Jackson-Pratt drain, which will be left near the site of resection.

Visit 4 (+1 day after Surgery): Day 2

- Hematology examinations, which includes: glucose, urea nitrogen, creatinine, sodium, potassium, calcium, total
 cholesterol, HDL and LDL, triglyceride, alkaline phosphatase, LDH, complete blood cell counts with differential and
 platelet counts, APTT, PT, INR, fibrinogen, VES, PCR
- · Liver function test examinations, which include: ALT, AST, ALP, bilirubin and total protein, gamma-GT
- Output (in ml) and characteristics of the perihepatic drains (drain pigmentation, i.e. biliary bloody clear)
- Concomitant medications recordings
- Adverse event assessments and recording

During the hospitalization the panel of the blood tests and of the liver function could be modified

Visit 5 (+2 days after Surgery): Day 3

- Hematology examinations, which includes: glucose, urea nitrogen, creatinine, sodium, potassium, calcium, total
 cholesterol, HDL and LDL, triglyceride, alkaline phosphatase, LDH, complete blood cell counts with differential and
 platelet counts, APTT, PT, INR, fibrinogen, VES, PCR
- Liver function test examinations, which include: ALT, AST, ALP, bilirubin and total protein, gamma-GT
- Output (in ml) and characteristics of the perihepatic drains (drain pigmentation, i.e. biliary bloody clear)
- Bilirubin concentration in the perihepatic drains, to detect the presence of any perihepatic collection
- Abdominal ultrasound, to detect the presence of any perihepatic collection
- Concomitant medications recordings
- · Adverse Event assessment and recording

During the hospitalization the panel of the blood tests and of the liver function could be modified.

Visit 6 (+3 to 6 days after Surgery): Day 4 to 6

- Hematology examinations, which includes: glucose, urea nitrogen, creatinine, sodium, potassium, calcium, total
 cholesterol, HDL and LDL, triglyceride, alkaline phosphatase, LDH, complete blood cell counts with differential and
 platelet counts, APTT, PT, INR, fibrinogen, VES, PCR
- Liver function test examinations, which include: ALT, AST, ALP, bilirubin and total protein, gamma-GT.
- Output (in ml) and characteristics of the perihepatic drains (drain pigmentation, i.e. biliary bloody clear)
- Timing of abdominal drainage removal, if applicable
- Concomitant medications recordings
- Adverse Event assessment and recording

During the hospitalization the panel of the blood tests and of the liver function could be modified.

Visit 7 (Follow-up at 30 days ± 2 days): Day 30

A follow-up visit is scheduled for each patient and it will be done after 30 days from the day of the surgery, with an acceptable time-window of ±2 days.

- Hematology examinations, which includes: glucose, urea nitrogen, creatinine, sodium, potassium, calcium, total
 cholesterol, HDL and LDL, triglyceride, alkaline phosphatase, LDH, complete blood cell counts with differential and
 platelet counts, APTT, PT, INR, fibrinogen, VES, PCR
- Liver function test examinations, which include: ALT, AST, ALP, bilirubin and total protein, gamma-GT.
- Output (in ml) and characteristics of the perihepatic drains (drain pigmentation, i.e. biliary bloody clear), if the drainage is still in place
- Timing of abdominal drainage removal, if applicable
- · Concomitant medications recordings
- · Adverse Event assessment and recording

Visit 8 (6-8 weeks after Surgery): End of Study Visit

- Hematology examinations, which includes: glucose, urea nitrogen, creatinine, sodium, potassium, calcium, total cholesterol, HDL and LDL, triglyceride, alkaline phosphatase, LDH, complete blood cell counts with differential and platelet counts, APTT, PT, INR, fibrinogen, VES, PCR
- Liver function test examinations, which include: ALT, AST, ALP, bilirubin and total protein, gamma-GT.
- Output (in ml) and characteristics of the perihepatic drains (drain pigmentation, i.e. biliary bloody clear), if the drainage is still in place
- Concomitant medications recordings
- · Adverse Event assessment and recording

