	In a recent published case report [14] the authors reported the feasibility in							
	using HEMOPATCH Sealing Hemostat® for the management of a myocardial							
	wound, performing the procedure on cardiopulmonary bypass, which meant							
	the patient had to be heparinized. Despite these major risk factors for							
	bleeding HEMOPATCH Sealing Hemostat® managed to contain bleeding and							
	seal the wound without needing any suture.							

[figure not shown]

	Primary Objectives						
	To explore whether Hemopatch can improve time to hemostasis						
TRIAL OBJECTIVES	Secondary objectives						
THIAL OBJECTIVES	To explore whether Hemopatch can:						
	reduce the post-operative complications						
	shorten the use of drainage tube after hepatic resection						
	Primary						
	Evaluated comparing the achievement of hemostasis within 3 minutes from the						
	application of the patch in two groups:						
	common surgical techniques + Hemopatch						
	2. common surgical techniques						
	Secondary						
ENDPOINTS	Evaluated comparing the following outcomes:						
LINDFORMIS	the total drainage volume						
	the timing of drainage removal						
	the measurement of total volume of transfused blood products						
	the bile leaks						
	any adverse event						
	the length of hospital stay						
	rate of post-operative mortality						
INCLUSION CRITERIA	 Signed and dated Informed Consent obtained prior to the inclusion in the trial Men and women of any ethnic origin aged 18-75 years Women with childbearing potential willing not to start a pregnancy during the course of the study (at least within the time period foreseen for the patch absorption, i.e. 6-8 weeks from the application of Hemopatch) Men having relationships with women with childbearing potential willing not to procure a pregnancy during the course of the study (at least within the time period foreseen for the patch absorption, i.e. 6-8 weeks from the application of Hemopatch) Patients undergoing liver resection for any underlying disease and with resectable mass. The list of the underlying diseases is the following (but might not be limited to): Hepatocellular carcinoma Hilar cholangiocarcinoma Adrenal cancer metastasis Breast cancer metastasis Colorectal cancer metastasis Biliary carcinoma Hemangioma Hepatic adenoma Focal nodular hyperplasia Unilocular hydatid cyst Multilocular hydatid cyst 						

1. Trauma surgery						
2. Active sepsis around the liver						

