7. STUDY TREATMENT

7.1 Treatment in study

Hemopatch is an EMA approved sealant for hemostasis. It consists of a soft, thin, pliable, flexible pad of collagen derived from bovine dermis, coated with NHS-PEG. The white, tissue-facing side is covered with a thin layer of NHS-PEG that provides firm tissue attachment, thus sealing the bleeding surface and inducing hemostasis simultaneously. Due to its flexible structure, the application of Hemopatch to the site where hemostasis is desired is easily controlled. For differentiation, the non-coated side is marked with blue squares of a biocompatible colorant.

Hemopatch will be supplied in the following size:

Hemopatch 45 x 90 mm

Hemopatch is intended as an haemostatic device for surgical procedures when control of bleeding by pressure, ligature or conventional procedures is either ineffective or impractical.

In contact with blood, collagen induces aggregation of platelets. Platelets deposit in large numbers on the collagen structure, degranulate, and release coagulation factors that, together with plasma factors, enable the formation of fibrin. The structure of Hemopatch provides a three dimensional matrix for the additional mechanical strengthening of the clot. The NHS-PEG coating of this device, when in contact with blood, enhances its tissue adhesion properties and seals the bleeding surface. When applied as recommended, Hemopatch is resorbed in 6 – 8 weeks with little tissue reaction.

Hemopatch is not intended to be used in pulsatile, severe bleedings. The use of Hemopatch is not recommended in the presence of an active infection. Hemopatch is not intended as a substitute for meticulous surgical technique and the proper application of ligatures or other conventional procedures for hemostasis. Hemopatch should be maintained dry prior to application [15].

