7.1.1 Application of Hemopatch

The investigator will select the appropriate size of the pad so that it overlaps the margins of the bleeding surface by about 1 cm. The pad may be cut to the desired size and shape. Dry gloves and surgical instruments (forceps, scissors) should be used to handle, cut and apply Hemopatch. Multiple pads may be used for larger bleeding surfaces. The investigator will apply the dry Hemopatch with the non-marked white surface contacting the bleeding area. A dry gauze or patty will be used and will be hold in place with gentle, uniform pressure over the entire pad surface for 2 minutes. When applying Hemopatch, the investigator should minimize contact with bloody surgical instruments, gauzes or gloves due to the affinity of collagen to blood. After 2 minutes, the investigator should gently remove the gauze or patty from the pad; gentle irrigation may also help in removing the gauze or patty without dislodging Hemopatch from the bleeding site. If the bleeding has not been satisfactorily controlled, Hemopatch can be removed, without tissue damage, up to 3 minutes from the time of the initial tissue contact. The investigator should not try to forcefully remove the pad.

The target bleeding site is defined as a bleeding site that, after 30 seconds of firm manual compression, has persistent bleeding requiring immediate attention. The investigator, an experienced hepatic surgeon, will define the bleeding source (arterial, venous, capillary), bleeding severity (oozing, middle or spurting) and the approximate area of bleeding site (cm², mean).

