11.5 Efficacy analyses

Responder definition

A patient is defined as "Responder" if he/she achieves hemostasis after 3 min. Time to haemostasis is defined as the time required to obtain successful haemostasis in a single bleeding site. At 3 min, the inspection will be made and, if haemostasis is not achieved, the treatment is considered failed and the patient will be defined as "Non-Responder". A patient assigned to the experimental arm (Hemopatch) for whom was not possible, for any reason, to proceed with the assigned treatment (i.e. has to be treated with the standard care) will be considered as "Randomization failure" and excluded from the ITT population.

In accordance with the primary objective of the study, the proportion of responder patients measured at treatment end (i.e. visit 3) will be the primary endpoint.

The treatment comparison will be performed by a χ^2 test.

The test will be two-sided and conducted at the standard 0.05 significance level

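### The 3-minute primary endpoint has no stated clock start in Arm A, because the protocol's only time zero is Hemopatch application

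*Protocol*

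**What the plan says.** Section 11.5 makes the responder proportion at Visit 3 the primary endpoint, compared by a two-sided chi-square test at 5%. It applies one failure rule to every patient: "At 3 min, the inspection will be made and, if haemostasis is not achieved, the treatment is considered failed". It names no event from which the 3 minutes run.

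The start is given in Section 5.2, in the paragraph on Arm B patients: "At the time point of application a stopwatch starts simultaneously (time zero". Application there means application of the pad. The Synopsis uses the same anchor for the whole comparison, counting from "application of the patch in two groups", although one of the two groups is common surgical techniques alone.

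For the control arm, Section 5.2 says: "Patients allocated to ARM A, will undergo the conventional hemostatic procedures". The rest of that sentence concerns the drain. Section 4.1 gives no start for either arm.

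Three other statements bear on what precedes the clock:

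- Section 5.2 describes Arm B patients as "treated conventionally with the adjunct of Hemopatch".
- Section 7.1.1: "The target bleeding site is defined as a bleeding site that, after 30 seconds of firm manual compression, has persistent bleeding".
- The Visit 3 list in Section 5.2 includes, without distinction of arm, "Evaluation of the appropriate target bleeding site in the hepatic parenchyma".

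Under Section 7.2 only the patient is blinded. Under Section 5.2 a delegated operator records the time, following the surgeon's observation.

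**The concern.** A yes/no outcome at a fixed time is comparable between arms only if the time is counted from comparable moments. Here the stated rule works in Arm B and cannot be applied literally in Arm A, so someone in theatre has to choose the control start, and that team knows the allocation. If the choice differs systematically from the Arm B anchor, the control patients have more or less than 3 minutes in which to succeed, and the chi-square test reads the difference in window as a difference in treatment.

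This is not a detail that can wait for the analysis plan. The protocol fixes an anchor that fits one arm, and a start that was neither defined nor timed during surgery cannot be reconstructed from the database.

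**Working it through.** **1. Is there a start for Arm A anywhere?**

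| Place | Start event given | Usable in Arm A? |
|---|---|---|
| Synopsis, endpoints | patch application, for both groups | No, there is no patch |
| Section 4.1 | none | No |
| Section 5.2, Arm B paragraph | patch application | No |
| Section 5.2, Arm A sentence | none | No |
| Section 7.1.1, target site | defines a site, not a time zero | Not stated |
| Section 11.5 | none | No |

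**2. The plan's own figure.** Inputs from Section 11.1: 66% v 34%, power 90%, 5% level, 49 per arm. With the pooled-variance formula, mean rate 0.50 and difference 0.32:

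n per arm = [1.960 × √(2 × 0.50 × 0.50) + 1.282 × √(0.66 × 0.34 + 0.34 × 0.66)]² / 0.32² = 49.2

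That is 50 per arm (100 in total) when rounded up, against 98 stated. Normal-approximation power at 49 per arm is 89.9%. Exact enumeration of the uncorrected chi-square test gives 90.5%. The sample size is sound on its inputs; the problem lies in the endpoint rule.

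**3. Illustration of an offset.** The protocol gives no distribution of time to hemostasis, so one is assumed: F(t) = 1 − exp(−(t/s)^k), with s set so that F(3) = 0.34. Shape k = 1 is a constant hazard, −ln(0.66)/3 = 0.1385 per minute. The range shown is k = 0.5 to 2.

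The one offset the documents can anchor is the 30-second compression in Section 7.1.1. By definition the target site is still bleeding at its end, and in Arm B it comes before the patch. If it fell inside the Arm A clock, control patients would have 3 − 0.5 = 2.5 minutes from the comparable moment. For k = 1:

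F(2.5) = 1 − exp(−0.1385 × 2.5) = 29.3%

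For k = 0.5 and k = 2 the rates are 31.6% and 25.1%.

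Exact enumeration, 49 per arm, uncorrected chi-square test, two-sided 5%:

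| Case | No offset | k = 1 | k = 0.5 to 2 |
|---|---|---|---|
| No true effect (Arm B 34%), Arm A window 2.5 min: significant for Hemopatch | 2.4% | 7.0% | 4.3% to 15.8% |
| Arm B 66%, Arm A window 2.5 min: power | 90.5% | 96.6% | 94.2% to 98.9% |
| Arm B 66%, Arm A window 3.5 min (pure assumption): power | 90.5% | 80.2% | 86.1% to 63.9% |

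In the last row the Arm A rate at 3.5 minutes is 38.4% for k = 1, 36.2% for k = 0.5 and 43.2% for k = 2. Nothing in the documents points to an offset in that direction; the row only shows that the sign matters.

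**The case against.** The strongest reply is that the intended start is easy to guess. Target-site evaluation is listed for all Visit 3 patients, the site is defined as one needing prompt attention, and Section 11.5 applies the 3-minute inspection to everyone. A surgeon would naturally start the Arm A clock when treatment of the verified site begins, in parallel with patch application in Arm B. This has force, and a reader should not infer that the endpoint is impossible to operate. The protocol does not state that reading, however, and does not say whether the compression or earlier conventional measures count. Section 7.1 describes the device as intended for bleeding "when control of bleeding by pressure, ligature or conventional procedures is either ineffective or impractical". That is general intended-use text and weak evidence about trial timing, but it does not close the gap.

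A reader might also infer that the trial is biased towards Hemopatch. The documents do not support this. They show no actual offset, and the 2.5-minute case is one possible reading. A longer control window would act the other way, though nothing in the text anchors one.

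A third inference would be that the clock should simply start at site confirmation. That would put pad selection, cutting and placement inside the Arm B clock, so it is not neutral between arms. It would also move the 3-minute point at which Section 5.2 permits additional measures, away from the limit for pad removal in Section 7.1.1, which runs from tissue contact.

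The loose wording elsewhere is minor: responders defined by hemostasis after rather than within 3 minutes, a misplaced time limit in Section 4.1, and a time interval called the endpoint in Sections 4.2 and 7.2. Section 11.5 makes the intent clear.

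**Conclusion.** The point holds. The protocol's only time zero is an event that Arm A never has, the Synopsis applies it to both groups, and no passage supplies a substitute. The primary-endpoint rule therefore cannot be applied to the control arm as written, and its start is left to an unblinded team. This conclusion rests on the text alone and needs no assumption.

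The size of any resulting bias is unknown. The offset figures depend on an assumed distribution and an assumed offset. They show only that a shift of half a minute is enough to matter at 49 per arm, and that the same short control window that inflates false positives also inflates apparent power. They do not predict what will happen in this trial, and the sample-size calculation is not in question.

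It should be corrected in the protocol, because the start has to be observed and recorded during surgery.

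**What to change.** Reconcile the Synopsis and Sections 4.1, 5.2 and 11.5 so that one start event begins the 3-minute clock. The sponsor and the investigator choose it; it must be observable in a comparable way in both arms.

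- State whether the 30-second compression, and any conventional measures given earlier at that site, count against the clock in each arm.
- Record the clock start and the 3-minute inspection in the eCRF for both arms.
- Check the chosen start against the other passages that count 3 minutes: additional measures in Section 5.2 and pad removal in Section 7.1.1. How these are reconciled is for the sponsor and the investigator.
- Use one wording, hemostasis within 3 minutes of time zero, in the Synopsis and Sections 11.1 and 11.5, and name the responder proportion as the endpoint in Sections 4.2 and 7.2.

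The cost is a protocol amendment, probably substantial under Section 12.2 because it affects scientific value. That means Ethics Committee review and notification of the Regulatory Authority (Sections 12.2 and 13.1), plus a few eCRF fields. The total of 98 stands if the 66% and 34% rates still apply under the chosen start; if that start changes what either rate measures, Section 11.1 needs to be revisited.

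### The 3-minute clock of the primary endpoint starts at patch application, so Arm A, which receives no patch, has no stated time zero

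*Protocol*

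**What the plan says.** The protocol gives two origins for the clock, and both are the patch.

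- The synopsis endpoint counts 3 minutes from the "application of the patch in two groups", the second of which receives conventional techniques only.
- Section 5.2, Visit 3, states for Arm B that "Hemopatch is applied upon the verification made by the surgeon of the presence of an appropriate target bleeding" site, and continues: "At the time point of application a stopwatch starts simultaneously (time zero". The time is "recorded by the operator delegated by the Principal Investigator and according to the" surgeon's observation.
- For Arm A, the same section says "Patients allocated to ARM A, will undergo the conventional hemostatic procedures" and that a drain is left. It mentions no stopwatch and no start.

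Three elements are not limited to one arm. The Visit 3 list includes "Evaluation of the appropriate target bleeding site in the hepatic parenchyma". Section 7.1.1 defines that site as one that, "after 30 seconds of firm manual compression, has persistent bleeding requiring immediate attention". Section 11.5 sets the 3-minute inspection and the failure rule for a patient in general. None of these says when the 3 minutes begin. Sections 4.1, 4.2 and 7.2 name a window or an interval, also without an origin.

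**The concern.** The responder proportion at 3 minutes is the only outcome with a formal test and a power statement. Comparing two such proportions is meaningful only if the 3 minutes are counted from equivalent events. As written, the origin cannot occur in Arm A, so someone in theatre has to supply one. Site confirmation, the first conventional measure and the completion of that measure are all plausible, and they would generally give different responder rates.

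Two features make this more than loose wording. First, blinding covers patients only (section 7.2), so the person starting the watch and the surgeon judging haemostasis both know the arm. Practice could also differ between the three surgical departments named in the synopsis. Second, section 5.2 has the time to haemostasis recorded, but neither the moment of site confirmation nor the moment the clock starts. A statistical analysis plan finalised before database freeze could not recover a start that was never standardised or written down.

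**Working it through.** **Step 1. Is there an Arm A start anywhere?**

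| Place in protocol | What it fixes | Start event for Arm A? |
|---|---|---|
| Synopsis, endpoints | 3 minutes from patch application, both groups | No: the event cannot occur |
| 4.1 | 3 minutes, named at the end of the Arm B clause | No |
| 4.2, 7.2 | Time interval to haemostasis | No |
| 5.2, Visit 3 | Stopwatch at application, within the Arm B paragraph | No |
| 7.1.1 | Target bleeding site (30 seconds of compression) | Not named as time zero |
| 11.5 | Inspection at 3 minutes, failure rule, any patient | No |

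**Step 2. Reproduce the planned size.** Inputs from section 11.1: 66% against 34%, 90% power, 5% level; section 11.5 makes the test two-sided. With pooled variance under the null and no continuity correction:

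n per arm = [1.960 × √(2 × 0.5 × 0.5) + 1.2816 × √(0.34 × 0.66 + 0.66 × 0.34)]² / 0.32² = (1.3859 + 0.8586)² / 0.1024 = 49.2

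This agrees with the stated 49 per arm (50 if rounded up). Exact binomial enumeration of the uncorrected chi-square test at 49 per arm gives 90.5% power. With 34% in both arms it rejects in 4.8% of trials, of which 2.4% favour Arm B. The sample size is not in question.

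**Step 3. Illustrate one unequal start.** The protocol gives neither a distribution of haemostasis times nor an offset, so these are assumptions:

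- haemostasis occurs at a constant rate once treatment of the site begins, and not before;
- 34% achieve it at 3 minutes on conventional treatment;
- the patch adds nothing;
- Arm B is timed from patch contact and has the full 3 minutes;
- Arm A's clock starts d minutes before its first measure, with d = 0.5 or 1.

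Rate: λ = −ln(1 − 0.34)/3 = 0.1385 per minute. Arm A's observed proportion is 1 − exp[−λ(3 − d)].

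- d = 0.5: 1 − exp(−0.346) = 0.293
- d = 1: 1 − exp(−0.277) = 0.242

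Exact enumeration against 0.34 in Arm B, 49 per arm:

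| Arm A start | Arm A | Arm B | Two-sided rejection | Of which favour the patch |
|---|---|---|---|---|
| Common start | 34% | 34% | 4.8% | 2.4% |
| 0.5 min early | 29% | 34% | 7.7% | 7.0% |
| 1 min early | 24% | 34% | 18.5% | 18.4% |

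If Arm A's clock started late instead, for example once the first measure was complete, the effect would depend on how haemostasis before the clock is scored. The protocol does not address this, so no figure is given for that direction.

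**The case against.** **The rule can be read sensibly.** Application could mean the start of whichever measure was allocated. Site evaluation, the site definition and the 3-minute failure rule already cover both arms, so only one element is missing. It is therefore too strong to infer that the endpoint cannot be measured at all in half the trial. The objection does not close the gap, however. The synopsis specifies the patch, the stopwatch sentence sits in the Arm B paragraph, and even the generous reading leaves open whether Arm A starts at the beginning or the end of a suture or ligature.

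**The offset may be small.** Section 7.1.1 describes the target site as needing immediate attention, which argues against a long gap before treatment. The 0.5 and 1 minute values are assumed. This stands, and it is why the figures are only an illustration.

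**Why not simply start at site confirmation?** Section 7.1.1 allows that "The pad may be cut to the desired size and shape", so preparation time could fall inside Arm B's window, and a reader might conclude that this start should be ruled out. The documents do not support that. At a constant rate, a delay of 0.5 or 1 minute in Arm B alone would lower its rate from 66% to 59% or 51%, and power to 73% or 42%. The same delay in both arms leaves power at 87% or 80%. Which delay pattern would occur is unknown, so confirmation remains a possible common anchor.

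**The trial is exploratory.** It still has one primary endpoint with a two-sided 0.05 test and a 90% power claim, and both presuppose the same 3 minutes in each arm.

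**Conclusion.** The point holds. The protocol states the origin of its primary-endpoint clock in a form that cannot be applied to Arm A, and no other section supplies one. A common start is therefore neither specified nor ensured, and the start used cannot be checked from the items that section 5.2 lists for recording.

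A reader might go further and infer that the trial is biased towards Hemopatch. The documents do not show that. The surgeons may in practice use equivalent starts, in which case the bias is nil, and an unequal start could work in either direction. The rise from 4.8% to 7.7% or 18.5% (from 2.4% to 7.0% or 18.4% in favour of the patch) applies only under a constant haemostasis rate, 34% at 3 minutes, an inert patch and an Arm A clock that runs 0.5 or 1 minute before treatment. It shows that a discrepancy of this length would matter with 49 patients per arm; it does not estimate what will happen. The finding itself rests on the wording and does not depend on these figures.

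**What to change.** Amend the synopsis endpoint and sections 4.1 and 5.2 as follows.

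1. Name one start event in the same words for both arms. For example: the first application of the allocated haemostatic measure to the target bleeding site, confirmed as in section 7.1.1. That is patch contact in Arm B and the first conventional measure in Arm A. Another event would serve if it is the same in both arms.
2. State in section 5.2 that the 3-minute inspection and failure rule apply to both arms, in line with section 11.5.
3. Record the site-confirmation time and the clock-start time in the eCRF at Visit 3.

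The cost is a protocol amendment and one or two eCRF fields. Under section 12.2 the amendment is probably substantial, since it touches the scientific value of the study, so it would need ethics committee evaluation and notification to the authority. The sample size stays at 98. If recruitment has begun, Arm A times already taken cannot be re-timed, which is a reason to act early.
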